2.2 Institutional Review Board/Independent Ethics Committee

Before study initiation, the investigator must have written and dated approval/favorable opinion from the IRB/IEC for the protocol, consent form, subject recruitment materials/process (eg, advertisements), and any other written information to be provided to subjects. The investigator or sponsor should also provide the IRB/IEC with a copy of the Investigator Brochure or product labeling, information to be provided to subjects and any updates.

The investigator or sponsor should provide the IRB/IEC with reports, updates and other information (eg, expedited safety reports, amendments and administrative letters) according to regulatory requirements or institution procedures.

2.3 Informed Consent

Investigators must ensure that subjects, or, in those situations where consent cannot be given by subjects, their legally acceptable representative, are clearly and fully informed about the purpose, potential risks, and other critical issues regarding clinical studies in which they volunteer to participate.

BMS will provide the investigator with an appropriate (ie, Global or Local) sample informed consent form which will include all elements required by ICH, GCP and applicable regulatory requirements. The sample informed consent form will adhere to the ethical principles that have their origin in the Declaration of Helsinki.

Investigators must:

1. Provide a copy of the consent form and written information about the study in the language in which the subject is most proficient prior to clinical study participation. The language must be non-technical and easily understood.
2. Allow time necessary for subject or subject's legally acceptable representative to inquire about the details of the study.
3. Obtain an informed consent signed and personally dated by the subject or the subject's legally acceptable representative and by the person who conducted the informed consent discussion.
4. Obtain the IRB/IEC's written approval/favorable opinion of the written informed consent form and any other information to be provided to the subjects, prior to the beginning of the study, and after any revisions are completed for new information.
5. If informed consent is initially given by a subject's legally acceptable representative or legal guardian, and the subject subsequently becomes capable of making and communicating their informed consent during the study, then consent must additionally be obtained from the subject.
6. Revise the informed consent whenever important new information becomes available that is relevant to the subject's consent. The investigator, or a person designated by the investigator, should fully inform the subject or the subject's legally acceptable representative or legal guardian, of all pertinent aspects of the study and of any new information relevant to the subject's willingness to continue participation in the study. This communication should be documented.

The consent form must also include a statement that BMS and regulatory authorities have direct access to subject records.

Subjects unable to give their written consent (eg, stroke patients, or subjects with severe dementia) may only be enrolled in the study with the consent of a legally acceptable representative. The subject must also be informed about the nature of the study to the extent

compatible with the subjects' understanding, and should they become capable, personally sign and date the consent form as soon as possible. The explicit wish of a subject unable to give his or her written consent, who is capable of forming an opinion and assessing this information to refuse participation in, or to be withdrawn from, the clinical study at any time should be considered by the investigator.

The rights, safety, and well-being of the study subjects are the most important considerations and should prevail over interests of science and society.

3 INVESTIGATIONAL PLAN

[figure not shown]
3.1 Study Design and Duration

Expected duration of the study, from first subject, first visit through last subject, last visit is approximately 8 months.

This study is designed to evaluate the safety of oral apixaban 2.5 mg BID following total knee and hip replacement surgeries. There are four study periods extending up to maximum duration of approximately 42 ± 2 days for the patients undergoing total knee replacement surgery and up to 65 ± 2 days for the patients undergoing total hip replacement surgery:

- A screening period, of up to 14 days prior to surgery
- An enrollment period: from 4 days before surgery to 1 day after surgery
- A treatment period: First dose, PO, starting 12 - 24 hours after completing skin wound closure, then BID for 35 ± 2 days for the subjects undergoing total hip replacement or 12 ± 2 days for the subjects undergoing total knee replacement.
- A 30-day follow-up period starting the day after the last dose of study medication.

Figure 3.1-1: Study Design

3.1.1 Screening

The screening period will begin with a screening visit that occurs up to 14 days prior to surgery. Subjects undergoing elective THR or TKR surgery (including revisions) who meet the inclusion/exclusion criteria are eligible for study entry.

No study-related procedure may be performed until the subject has been completely informed of the study, has freely consented to take part in the study, and has signed and dated an informed consent document approved by a licensed Institutional Review Board (IRB) or Independent Ethics Committee (IEC).

Blood sample and Urine pregnancy test will be collected for laboratory assessments.

The IVRS system will be contacted to obtain a unique subject number. Medical history, vital signs and body weight will be obtained (refer to [Section 5.1](#) for details).

3.1.2 Enrollment

The enrollment may occur from 4 days prior to surgery to 24 hours after surgery.

Subjects who meet all the inclusion/exclusion criteria will be enrolled to the site for this visit. Subjects (N = 500) will be assigned to oral apixaban 2.5 mg BID

Blood sample and Urine pregnancy test will be collected for laboratory assessments.

Sites will call into the IVRS system for assignment to apixaban 2.5 mg; sites will indicate whether the subject is undergoing either a TKR or THR. Either hip or knee replacement patients may be enrolled in any order, but BMS may place enrollment limits on either type of surgical patient to ensure adequate enrollment of both knee and hip surgery patients in the study.

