4.2 Method of Assigning Subject Identification

At screening, each subject will be assigned a unique sequential number by the Interactive Voice Response System (IVRS). The IVRS will be available 24 hours per day, seven days a week. The subject number will consist of a unique 5-digit number which is assigned sequentially within a study (starting with 00001) by the IVRS. This number will be used for identification throughout the study and will not be used for any other subject.

After meeting inclusion/exclusion criteria, subjects eligible for the treatment will be assigned prior to surgery to apixaban 2.5 mg by the IVRS.

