5 STUDY ASSESSMENTS AND PROCEDURES

5.1 Flow Chart/Time and Events Schedule

Table 5.1-1: Screening Procedural Outline for TKR Subjects (CV185158)

Procedure - TKR Subjects	Screening Visit	Enrollment	Treatment Period					Follow up Period	Notes
			Surgery	Day 2	Hospital Discharge	Day 7	Day 12		
Days	Pre-Surgery 1-14	Pre-Surgery -4 days to +24 hours	Surgery Day 1	Day 2	Hospital Discharge	Day 7 ± 2 days	Day 12 ± 2 days	Day 42 ± 2 days	
Informed Consent	X								
Inclusion/Exclusion Criteria	X								
Medical History	X								
Weight & Age & Gender	X								
Vital Signs (SBP/DBP & HR)	X								
Contact IVRS	X	X							At screening, after obtaining signed informed consent form, contact IVRS to obtain subject number; At enrollment, contact IVRS for assignment to apixaban 2.5 mg
Dispense Study Medication			X						
Discharge Instructions					X				
Review Medication Compliance					X	X	X		
AE/SAE Assessment		X	X	X	X	X	X	X	Lab: for SAE's related to liver failure/jaundice/hepatitis: local lab hepatitis panels and full LFT's (AST, ALT, T.Biliruin, D. bilirubin, GGT, AP, PT/aPTT/INR) must be performed; for bleeding related

Table 5.1-1: Screening Procedural Outline for TKR Subjects (CV185158)

Procedure - TKR Subjects	Screening Visit	Enrollment	Treatment Period					Follow up Period	Notes
			Surgery Day 1	Day 2	Hospital Discharge	Day 7 ± 2 days	Day 12 ± 2 days		
Days	Pre-Surgery 1-14	Pre-Surgery -4 days to +24 hours	Surgery Day 1	Day 2	Hospital Discharge	Day 7 ± 2 days	Day 12 ± 2 days	Day 42 ± 2 days	SAE's, analysis of CDC, PT/aPTT/INR must be performed by the local lab.
Symptomatic VTE Assessment		X	X	X	X	X	X	X	
Local Lab: Serum Creatinine LFT's (AST, ALT, TBIL) & CBC	X	X							
Local Lab: Hb	X	X			X				
Dosing Diaries to be collected						X	X		
Pregnancy Test	X	X			X		X		

Table 5.1-2: Screening Procedural Outline for THR Subjects (CV185158)

Procedure - THR Subjects	Screening Visit	Enrol-ment	Treatment Period					Follow up Period	Notes
Days	Pre-Surgery 1-14	Pre-Surgery -4 days to +24 hours after surgery	Surgery Day 1	Day 2	Hospital Discharge	Day 7 ± 2 days	Day 35 ± 2 days	Day 65 ± 2 days	
Informed Consent	X								
Inclusion/Exclusion Criteria	X								
Medical History	X								
Weight & Age & Gender	X								
Vital Signs (SBP/DBP & HR)	X								
Contact IVRS	X	X							At screening, after obtaining signed informed consent form, contact IVRS to obtain subject number; At enrollment, contact IVRS for assignment to apixaban 2.5 mg
Dispense Study Medication			X						

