### 2.1 Study Design

Expected duration of the study, from first subject, first visit through last subject, last visit is approximately 8 months.

This study is designed to evaluate the safety of oral apixaban 2.5 mg BID following total knee and hip replacement surgeries. There are four study periods extending up to maximum duration of approximately  $42 \pm 2$  days for the patients undergoing total knee replacement surgery and up to  $65 \pm 2$  days for the patients undergoing total hip replacement surgery:

- A screening period, of up to 14 days prior to surgery
- An enrollment period: from 4 days before surgery to 1 day after surgery
- A treatment period: First dose, PO, starting 12 - 24 hours after completing skin wound closure, then BID for  $35 \pm 2$  days for the subjects undergoing total hip replacement or  $12 \pm 2$  days for the subjects undergoing total knee replacement.
- A 30-day follow-up period starting the day after the last dose of study medication.

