### **7.6.2 Laboratory Data**

Refer to Section 7.6.2.2 in the Core SAP for VTE Prevention. Hemoglobin is the parameter which will be summarized.

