**Table 8.3A: Day Ranges for summary of Laboratory Measurements**

Nominal Visit	Target Day	Day Ranges
Screening	Pre-Surgery 1-14 day	Screening to < Enrollment
Enrollment	Pre-Surgery -4 day - 24 hours	Enrollment to < start of surgery
Hospital discharge	Hospital discharge	Day 2 to < End of treatment period

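### Enrollment is allowed up to 24 hours after surgery, but Protocol 4.2 assigns subjects before surgery and the SAP Table 8.3A Enrollment range stops at surgery, so a post-operative enrollment hemoglobin has no correct row

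*Protocol*

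**What the plan says.** **Enrollment window.** Protocol 3.1.2 states: "The enrollment may occur from 4 days prior to surgery to 24 hours after surgery". The synopsis, Protocol 3.1 and the Enrollment column heads of Tables 5.1-1 and 5.1-2 give the same window; the hip table reads "Pre-Surgery -4 days to +24 hours after surgery". SAP 2.1 repeats it: "An enrollment period: from 4 days before surgery to 1 day after surgery". That makes six statements allowing enrollment up to 24 hours, or one day, after surgery.

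**Assignment.** Protocol 4.2 says that eligible subjects "will be assigned prior to surgery to apixaban 2.5 mg by the IVRS". The notes to both schedules, and Protocol 3.1.2, make the IVRS call at enrollment the call that assigns apixaban.

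**Samples.** Both schedules mark hemoglobin at Screening, Enrollment and Hospital Discharge.

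**Laboratory ranges.** SAP Table 8.3A has three rows. Screening runs up to, but not including, enrollment. Enrollment has the target day "Pre-Surgery -4 day - 24 hours" and the range "Enrollment to < start of surgery". Hospital discharge has the range "Day 2 to < End of treatment period". Protocol 3.1.3 numbers the day of surgery as Day 1.

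**Use of the ranges.** SAP 8.3 gives them as the ranges for laboratory summaries, and SAP 7.6.2 says: "Hemoglobin is the parameter which will be summarized".

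**The concern.** A site that enrolls a subject on the evening of surgery complies with Protocol 3.1.2 and breaches Protocol 4.2. Enrollment and assignment cannot be separated to avoid this, because the schedules make them the same IVRS call.

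The laboratory table then has no suitable place for the sample taken at that enrollment. The Enrollment range closes before it opens, and the Hospital discharge row opens by calendar day, not by dose. A Day 2 sample taken before the first tablet would therefore be summarized alongside on-treatment discharge values. What is at stake is a clean reading of hemoglobin before surgery, after surgery without drug, and at discharge, for the one laboratory parameter that the SAP names for summary.

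**Working it through.** No sample-size or power figure bears on this point. The check places each possible enrollment-visit sample against the three ranges in SAP Table 8.3A.

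Inputs:
- the enrollment window (Protocol 3.1.2);
- Day 1 as the day of surgery (Protocol 3.1.3);
- the first dose 12 to 24 hours after wound closure (Protocol 3.1.3);
- the three ranges (SAP Table 8.3A).

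Because the ranges turn on the time of enrollment, the order of blood draw and IVRS call matters.

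| Enrollment-visit hemoglobin drawn | Screening row | Enrollment row | Hospital discharge row | Placement |
|---|---|---|---|---|
| 48 h before surgery, at the call | no | yes | no | Enrollment (correct) |
| After surgery, Day 1, at or after the call | no | no | no | No row |
| After surgery, Day 2, at or after the call | no | no | yes | Hospital discharge only |
| After surgery, Day 1, just before the call | yes | no | no | Screening |
| After surgery, Day 2, just before the call | yes | no | yes | Two rows |

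No post-operative case reaches the Enrollment row. The last two rows label a post-operative value as screening, which is also wrong.

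**How the 24-hour window splits.** Assume a two-hour operation starting at clock hour S (neither is in the documents). The post-operative window opens at S + 2, so 24 − (S + 2) = 22 − S hours of it lie on Day 1, and the other 24 − (22 − S) = S + 2 hours on Day 2.
- S = 8: 14 hours on Day 1, 10 on Day 2.
- S = 12: 10 and 14.
- S = 16: 6 and 18.
- S = 20: 2 and 22.

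Both misplacements are therefore possible for ordinary operating times. These are lengths of time, not frequencies of enrollment.

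**Per-subject size.** A subject enrolled after surgery, with the Enrollment sample drawn then, has 1 of 3 scheduled hemoglobin samples without a correct row. A subject enrolled before surgery has 0 of 3.

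**Day 2 and dosing.** With the first dose at 12 to 24 hours after closure, a Day 2 enrollment draw can precede it. Conversely, the compliance formula in SAP 7.4.1 allows for a first dose on the day of surgery. A Day 1 value after such a dose would also miss the Hospital discharge row.

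**The case against.** The strongest reply is that this is an editorial mismatch with no demonstrated effect. If sites follow Protocol 4.2, nobody enrolls after surgery and every sample has its row. There are signs of that intent: the synopsis has sites record the planned surgery, and both schedules mark dispensing in the Surgery Day 1 column, after the Enrollment column. Counting six statements against one also overstates the weight of evidence, since SAP 2.1 repeats Protocol 3.1 and the two schedules share a template. This stands as a reason for a low grade. It does not remove the conflict, because sites are told in several places that they may enroll after surgery.

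A second reply is that much is deferred to the Core SAP: laboratory data, safety conventions, baseline and multiple measurements (SAP 7.6.2, 8.1, 8.2, 8.4). A multiple-measurement rule would only choose among values within a row. A rule for out-of-window values, or one that files samples by nominal visit, could resolve the placement. That stands, so the placements above are what Table 8.3A gives on its own terms.

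Two stronger readings are tempting.
- **That the primary endpoint is compromised**, because a hemoglobin fall of 2 g/dL is part of the major bleeding definition. The documents do not support this: bleeding events are adjudicated by the committee, and Table 8.3A is stated to govern laboratory summaries only.
- **That the table's Enrollment row contradicts itself.** Its target day, "Pre-Surgery -4 day - 24 hours", may echo the protocol window, but it can also mean from 4 days to 24 hours before surgery, which would fit its range. It is ambiguous, not clearly contradictory.

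**Conclusion.** The point holds in limited form. Protocol 4.2 conflicts with the enrollment window stated elsewhere, and the Enrollment range in SAP Table 8.3A cannot receive a sample from a subject enrolled after surgery.

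The exposure is confined to the descriptive hemoglobin summary. The number of subjects is not given, may be zero, and is zero if Protocol 4.2 is followed. The conclusion assumes that samples are filed by the ranges in Table 8.3A and that the unseen Core SAP does not override them. It is a correction worth considering because it is specific and cheap, not because it threatens the trial's main result.

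**What to change.** 1. **Protocol 4.2.** Make it agree with 3.1.2: IVRS assignment takes place at enrollment, from 4 days before to 24 hours after surgery, and before study drug is dispensed or taken.
2. **SAP Table 8.3A, Screening and Enrollment.**
   - End the Screening row at the earlier of enrollment and start of surgery.
   - Keep a pre-operative Enrollment row from enrollment to before the start of surgery.
   - Add a post-operative Enrollment row from end of surgery to before the first dose. Limit it to Enrollment-visit samples from subjects enrolled after surgery, so that unscheduled post-operative values from subjects enrolled earlier are not labelled as enrollment.
   - Write the target day as −4 days to +24 hours.
3. **SAP Table 8.3A, Hospital discharge.** Start the row at the first dose instead of Day 2. This also covers a first dose on the day of surgery.
4. **Pre-surgical value.** Unless Core SAP 8.2 already says so, define pre-surgical hemoglobin as the last value before the start of surgery.

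Under these rows each of the five cases in the table above falls in exactly one Enrollment row, whichever comes first, draw or call, provided the post-operative draws precede the first dose.

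The cost is one phrase in Protocol 4.2, one added row and a few edited cells in Table 8.3A, and one definition. No visit or sample is added. The enrollment window in 3.1.2 is unchanged, but if the sponsor has been treating 4.2 as binding, item 1 does open post-operative assignment. In that case the sponsor should decide which rule it wants. Closing enrollment at surgery is a defensible alternative, but it means changing the six statements instead of the one.

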3.1.3 Treatment Period

The day of surgery is Day 1.

The first dose of apixaban will be administered 12 - 24 hours after completing skin wound closure, typically in the morning of Day 2 and then BID for 35 ± 2 days for the subjects undergoing total hip replacement or 12 ± 2 days for the subjects undergoing total knee replacement.

While hospitalized, subjects will be evaluated on Day 1, Day 2 and discharge day for suspected symptomatic VTE, bleeding events or any AEs or SAEs.

At any subsequent treatment visits (Day 7 ± 2 and Day 12 ± 2 for TKR subjects or Day 7 ± 2 and Day 35 ± 2 for THR subjects), subjects will be instructed to report to the investigator all AEs, including signs and/or symptoms suggestive of VTE and any bleeding events they experienced since their last visit. Subjects with signs and/or symptoms of VTE at any time should return to the hospital/clinic and undergo appropriate diagnostic evaluation.

If study medication is discontinued for a suspected DVT and or PE, alternative antithrombotic prophylaxis may be initiated per the Investigator's discretion and standard of care. Every effort

must be made to confirm a suspected DVT and/or PE diagnosis before discontinuing study medication and initiating treatment per the Investigator's standard of care.

Samples for laboratory assessment of hematology will be obtained on the day of discharge.

Urine pregnancy test will be performed on Day 12 for TKR subjects and on Day 35 for THR subjects.

Dosing Diaries should be collected at Day 7 & Day 12 for TKR subjects and at Day 7 & Day 35 for THR subjects.

Subjects should be encouraged to return for an in person visit on Day 7 and Day 12 for TKR and Day 7 and Day 35 for THR. Alternatively those visits would be performed by phone.

3.1.4 Follow-up Period

As appropriate and per the Investigator's discretion and standard of care, alternative antithrombotic prophylaxis may be initiated the day after the last dose of study medication.

For subjects undergoing TKR surgery, follow-up study visit will occur on Day 42 ± 2 and for subjects undergoing THR surgery, the follow up visit will occur on Day 65 ± 2. Subjects should be encouraged to return for an in person follow up visit at Day 42 (TKR) or Day 65 (THR). Alternatively those visits would be performed by phone.

Subjects will be asked to report to the Investigator, all AEs/SAEs including those symptoms suggestive of DVT and/or PE and bleeding. Suspected DVT and/or PE will be evaluated using the appropriate diagnostic assessment.

3.2 Post Study Access to Therapy

At the end of the study, the sponsor will not continue to supply study drug to subjects/investigators unless the sponsor chooses to extend the study. The investigator should ensure that the subject receives appropriate standard of care to treat the condition under study.

3.3 Study Population

For entry into the study, the following criteria MUST be met.

3.3.1 Inclusion Criteria

1) Signed Written Informed Consent

- a) Age ≥ 18 years
- b) Subjects must be willing and able to give written informed consent. Consent to participate in the study must be obtained prior to any screening procedures.

2) Target Population

- a) Subjects undergoing elective total knee or hip replacement or a revision of at least one component of a total knee or hip replacement.

3) Age and Reproductive Status

- a) Women of childbearing potential (WOCBP) and men must be using an acceptable method of contraception to avoid pregnancy throughout the study in such a manner that the risk of pregnancy is minimized. See [Section 3.3.3](#) for the definition of WOCBP.
- b) WOCBP must have a negative serum or urine pregnancy test (minimum sensitivity 25 IU/L or equivalent units of HCG) within 24 hours prior to the start of investigational product.
- c) Women must not be breastfeeding
- d) Sexually active fertile men must use effective birth control if their partners are WOCBP.

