3.3.2 Exclusion Criteria

1) Target Disease Exceptions

- a) Known or suspected, acquired or bleeding or coagulation disorder in the subject or a first degree relative
- b) Known coagulopathy
- c) Active bleeding or at high risk for bleeding.

2) Medical History and Concurrent Diseases

- a) Brain, spinal, ophthalmologic, or major surgery or trauma within the past 90 days
- b) Active hepatobiliary disease
- c) Alcohol and/or substance abuse within the past year
- d) Any condition, in the opinion of the Investigator, for which surgery or administration of an anticoagulant is contraindicated.

3) Physical and Laboratory Test Findings

- a) Two consecutive blood pressure readings within 15-30 minutes with supine SBP > 180 mm Hg or supine DBP > 105 mm Hg
- b) Hemoglobin < 9 g/dL
- c) Platelet count < 100,000/mm³
- d) Creatinine clearance < 30 mL/min as estimated by the method of Cockcroft and Gault
- e) Active hepatobiliary disease, based on an ALT or AST > 2 x ULN or a Total Bilirubin ≥ 1.5 x ULN (unless an alternative causative factor [eg, Gilbert's syndrome] is identified).

4) Sex and Reproductive Status

- a) WOCBP who are unwilling or unable to use an acceptable method to avoid pregnancy for the entire treatment period of the study

- b) Women who are pregnant or breastfeeding
- c) Women with a positive pregnancy test on enrollment or prior to investigational product administration.

5) Other Exclusion Criteria

- a) Prisoners or subjects who are involuntarily incarcerated
- b) Subjects who are compulsorily detained for treatment of either a psychiatric or physical (eg, infectious disease) illness
- c) Administration of any investigational drug currently or within 30 days prior to enrollment into this study.

6) Prohibited Treatments and/or Therapies

- a) Any antiplatelet agents (including clopidogrel) other than aspirin
- b) Vitamin K antagonist or other novel oral anticoagulant (such as rivaroxaban or dabigatran) during the treatment period
- c) Ongoing unfractionated heparin or low molecular weight heparin use
- d) Use of thrombolytics within past 7 days
- e) Use of Fondaparinux

Eligibility criteria for this study have been carefully considered to ensure the safety of the study subjects and to ensure that the results of the study can be used. It is imperative that subjects fully meet all eligibility criteria.

3.3.3 *Women of Childbearing Potential*

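### The visit schedule does not deliver the pregnancy test that inclusion 3b requires: the last scheduled pre-dose test can be about 4.5 to 5 days old against a 24-hour limit

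*Protocol*

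**What the plan says.** Inclusion 3b in Protocol section 3.3.1 requires a woman of childbearing potential (WOCBP) to have a negative serum or urine test "within 24 hours prior to the start of investigational product". Exclusion 4c in section 3.3.2 bars "Women with a positive pregnancy test on enrollment or prior to investigational product administration". Section 3.3.2 closes by insisting that every eligibility criterion be fully met.

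The timing is set elsewhere:

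- Section 3.1.2: "The enrollment may occur from 4 days prior to surgery to 24 hours after surgery". At that visit, "Blood sample and Urine pregnancy test will be collected for laboratory assessments".
- Section 3.1.3: "The first dose of apixaban will be administered 12 - 24 hours after completing skin wound closure", typically on the morning of Day 2. The only pregnancy tests this section names are on Day 12 (knee) and Day 35 (hip).
- Section 4.2: "subjects eligible for the treatment will be assigned prior to surgery to apixaban 2.5 mg by the IVRS".
- Section 5.1: Table 5.1-1 heads the Enrollment column "Pre-Surgery -4 days to +24 hours", and Table 5.1-2 gives the same window. In both tables the "Pregnancy Test" row is marked at Screening, Enrollment, Hospital Discharge and Day 12 or Day 35. The Day 1 and Day 2 cells are empty. The inclusion/exclusion row is marked at Screening only.

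**The concern.** Criterion 3b is tied to the first dose, but the schedule is tied to enrollment, and the two can be days apart. The Hospital Discharge column comes after Day 2, so the discharge test normally follows the first dose. That leaves the Enrollment test as the last scheduled check before exposure. No table note or visit text says that this test may have expired by the time of dosing. The tables mark eligibility review only at Screening, when 3b cannot yet be judged.

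Sites work from the schedule tables. A site that tests only at the tabulated visits can dose a woman who does not meet a mandatory safety criterion. At stake are exposure in an undetected early pregnancy and avoidable eligibility deviations. The bleeding estimate and its precision are not at stake.

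**Working it through.** **Inputs**

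- Maximum age of the test at first dose: 24 h (section 3.3.1, 3b).
- *a*, hours from the Enrollment test to the start of surgery: 0 to 96 for enrollment before surgery (section 3.1.2; Tables 5.1-1 and 5.1-2).
- *t*, hours from wound closure to first dose: 12 to 24 (section 3.1.3).
- *D*, operating time to wound closure: not stated in the documents. It is assumed to be 0 to 3 h, with 0 as the limiting case most favorable to the plan.

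**Age of the Enrollment test at first dose** = *a* + *D* + *t*. Each range below runs from *t* = 12 to *t* = 24.

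| Test before surgery (*a*) | Age, *D* = 0 | Age, *D* = 3 h | Can 3b be met? |
|---|---|---|---|
| 96 h | 108–120 h | 111–123 h | No |
| 72 h | 84–96 h | 87–99 h | No |
| 48 h | 60–72 h | 63–75 h | No |
| 24 h | 36–48 h | 39–51 h | No |
| 12 h | 24–36 h | 27–39 h | Only if *D* = 0 and *t* = 12 |
| 6 h | 18–30 h | 21–33 h | With early dosing |
| 0 h | 12–24 h | 15–27 h | Usually; not if *D* + *t* exceeds 24 |

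At day -4 the test is 108/24 = 4.5 to 120/24 = 5.0 days old, plus operating time. That is 4.5 to 5 times the limit.

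**When a pre-surgery Enrollment test complies.** Criterion 3b needs *a* + *D* + *t* ≤ 24, so *a* ≤ 24 − *t* − *D*. For any *D* > 0:

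- *t* = 12: *a* < 12 h, which is less than 12/96 = 12.5% of the pre-surgery enrollment hours.
- *t* = 18: *a* < 6 h, less than 6/96 = 6.25%.
- *t* = 24: *a* ≤ −*D*, so no pre-surgery time complies.

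With *D* assumed to be 1 to 3 h, the *t* = 12 limit becomes 9 to 11 h, or 9.4% to 11.5% of the 96 hours.

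**Which side of surgery.** Section 4.2 puts assignment before surgery, and the tables place the assignment call at Enrollment. SAP Table 8.3A also ends the enrollment laboratory window at the start of surgery. Pre-surgery enrollment is therefore the expected route, although section 3.1.2 also allows the 24 hours afterwards.

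**Check of the remedy.** For a test taken *s* hours after wound closure and before the first dose, the age at dosing is *t* − *s* ≤ 24 h. It complies at every permitted enrollment and dosing time.

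**The case against.** The strongest reply is that the safeguard already exists. Criteria 3b and 4c bind the site, section 3.1.2 enrolls only subjects who meet all criteria, and a site that respects 3b will repeat the test whatever the table shows. This stands as far as it goes: the requirement is not missing. But 4c excludes a positive result without scheduling a test. Nor can an eligibility check at an early enrollment confirm a condition defined by a dose still days away.

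Second, the enrollment window runs to 24 hours after surgery, and any test between wound closure and the first dose complies. This also stands, and the percentages above cover pre-surgery tests only. Counting all hours from day -4 to the first dose, the compliant share is 24/(96 + *D* + *t*). With *D* = 0 that is 24/108 = 22% at *t* = 12 and 24/120 = 20% at *t* = 24, so it does not fall to zero. None of these shares is a breach rate, because sites choose when to test.

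Third, 4.5 to 5 days is the extreme. That is correct, but a test one day before surgery is already 36 to 48 hours old at dosing, so the problem is not confined to day -4.

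Fourth, few women are involved, and they also have contraception requirements and normally two earlier negative tests. The risk is indeed small. The count may be somewhat larger than expected, though: under section 3.3.3 a woman below 62 with 12 months' amenorrhea counts as postmenopausal only with a documented FSH result (hormone replacement therapy aside), and neither table schedules one.

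Finally, the tables were read from PDF, and the WOCBP note in the hip table sits in the wrong column. Both tables nevertheless show the same pattern, and sections 3.1.1 to 3.1.3 name no Day 1 or Day 2 test either.

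**Conclusion.** The concern holds. The schedule as written does not guarantee the test that 3b makes mandatory. In the worst permitted case the last scheduled pre-dose test is 108 to 120 hours old plus operating time, against 24 hours. For enrollment before surgery, the scheduled test satisfies 3b only in the last 12 hours or less before the operation.

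This rests on three things: the Enrollment test is not repeated, discharge follows the first dose, and operating time is greater than zero. The documents give neither the number of WOCBP nor the distribution of enrollment times, so the number of women who would be dosed without a valid test cannot be estimated; it is likely small and could be zero. This is a matter of subject safety and protocol compliance and should be corrected. It has no bearing on the primary analysis.

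**What to change.** - In Tables 5.1-1 and 5.1-2, add a WOCBP-only urine or serum pregnancy test on Day 1 after wound closure or on Day 2 before dosing, within 24 hours before the first apixaban dose.
- In section 3.1.3, add a sentence requiring a negative result from that test before the first dose is given.
- In section 3.1.2, state that the Enrollment test counts toward 3b only if it falls within the 24 hours before the first dose.

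The cost is one row edit in each table and one sentence in each of the two sections. In conduct it means one added or re-timed test in a probably small, unstated number of women, at visits already scheduled. Criterion 3b already demands that test, so the change adds no new requirement.
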